Study procedures: will be performed according to the study procedure timeline (*Figure 8*, which includes both phases of the study). All cardiac and vascular measures will be analyzed blinded to dietary assignment, food diary results, 24-hour BP, and urinary electrolytes; 1/10 of cardiovascular studies will be re-analyzed by a second investigator to establish reproducibility and rigor of results. All study data will be recorded in REDCap, a secure research web application, under a unique study ID number assigned to participants.

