- Blood tests: *Screening*: comprehensive metabolic panel, complete blood count, B-type natriuretic peptide (BNP), hemoglobin A1C, lipid panel. *All other visits*: basic metabolic panel, insulin, BNP, F2-isoprostanes, aldosterone, IL-6, hs-CRP, TNF-α. These measures were chosen to evaluate the effects of DASH/SRD on renal function, electrolytes, renin-angiotensin-aldosterone system, insulin resistance, and oxidative stress, as well as inflammation markers previously associated with incident HFpEF (Kalogeropoulos et al. 2010). A repeat lipid panel will also be obtained at the end of the study. Whole-blood samples will be used for the mini-SBT (see *Aim 3* for description). Additional samples will be stored for post-hoc biomarker analysis, planned to include syndecan-1 and heparan sulfate, serological markers of endothelial glycocalyx degradation, and the adipokines leptin, adiponectin, and resistin.
- 24-hour urine: All collections: sodium, potassium, creatinine, aldosterone, F2-isoprostanes, and microalbumin. These measures were selected to assess DASH/SRD adherence, the relationship between systemic oxidative stress and renin-angiotensin-aldosterone system activation in salt-sensitive and resistant subjects (Al-Solaiman et al. 2009), and chronic microvascular damage. Additional samples will be

- stored for post-hoc analysis of biomarkers. The completeness of 24-hour urinary collections will be assessed via creatinine excretion per the method of Knuimann et al. (Murakami et al. 2008).
- Dietary assessment: Estimated nutrient intakes from the Block Food Frequency Questionnaire (collected at screening and at the end of study) will be analyzed (NutritionQuest, Berkeley, CA) and scored for DASH/SRD concordance (Mellen et al. 2008). Three-day food diaries will be performed during weeks 2 and 4 of *Phase 1* (i.e., the final week of usual diet and home-delivered DASH/SRD) and at Month 1 and Month 6 of *Phase 2*; these will be initially reviewed for completeness by the study dietitian and analyzed with Nutrition Data System for Research (2015 version; Nutrition Coordinating Center, Minneapolis, MN) through the Michigan Nutrition Obesity Center (MNORC);

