Phase 2 data collection: History and exam, questionnaires, blood tests, 24-hour BP and urine collections will be performed at months 1 and 6 of Phase 2 (see Study procedures above). Dietary concordance with DASH/SRD, the measure of exposure in Phase 2, will be assessed via Block Food Frequency Questionnaire and 24-hour urine sodium excretion at month 6, and 3-day food diaries immediately prior to the Month 1 and Month 6 visits. Arterial tonometry, echocardiography, SDF microscopy, and the mini-SBT will be performed at Month 6 of Phase 2 (see also Figures 7 and 8). Following Phase 2, participants will have follow-up after 6 months via telephone interview to assess cardiovascular events and vital status; subjects will be mailed a Food Frequency Questionnaire to evaluate persistence of dietary patterns after study participation; and there may be an optional in-person visit determined by study staff, based on need, for an additional arterial tonometry procedure and blood pressure check.

Dietary intervention: Phase 2 of the protocol will begin within 2 weeks of the end of Phase 1, and typically will begin immediately (i.e., as part of the week 4 visit). During this period, participants will be placed back on their prior antihypertensive therapy, if any, under [name] guidance. Prior to the first Phase 2 visit, subjects will be randomized to control (motivational interviewing only) or the addition of the WHEELS-I program. At the first visit of Phase 2, participants will update their cognitive representation of the DASH/SRD, and have an inperson dietitian session during which motivational interviewing techniques will be employed to explore and support willingness to change dietary habits. If the participant desires, the motivational interviewing portion of the visit may be conducted by telephone. Motivational interviewing-based counseling will continue via telephone during week 2, month1 visit, and at months 2 and 4.

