The WHEELS-I program consists of three daily activities: in the morning, reading messages that reinforce the key DASH/SRD diet educational components (e.g., types of foods, number of servings, rationale for recommendations) related to a specific dietary goal, then brief journaling of emotions and thoughts related to this goal; in the evening, record of DASH/SRD adherence during that day. An example: goal, eat 4-5 servings of fruits and vegetables per day; messages, try fresh fruits in season, make a fruit salad of "light" or "natural juice" canned fruits, keep dried fruits in your desk or car for snacks; journaling, "I am learning to appreciate the

sweetness of fruit." The daily activities are designed to take less than five minutes. Participants assigned to the WHEELS-I program may choose whether to receive messages via email, in identical fashion to the study shown in the *Preliminary Data* above, or via a newly created smartphone mobile application. Both methods will link to the same web-based information and surveys, which will collect data and store it under subject number in the Amazon.gov cloud storage system, where data will be accessible only by study personnel.

For the first 30 days of *Phase 2*, WHEELS-I participants will receive a structured series of messages that cycle through the DASH/SRD goal areas, e.g. increasing consumption of fruits and vegetables, whole grains, nuts and legumes, and low-fat dairy and reducing intake of sodium, red meat, and sweets. At the Month 1 dietitian visit, all participants will again update their DASH/SRD cognitive representation. Those assigned to WHEELS-I will then decide how frequently to receive morning messages for the next 30 days (evening messages will continue for the next 60 days). Options will include 1) continue daily morning messages, 2) morning messages three times a week, 3) morning messages once a week.

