These ongoing messages will be tailored toward challenges identified through motivational interviewing sessions and updating of the DASH/SRD cognitive representation. Message tailoring is a process that includes 1) assessment of individual characteristics relevant to a particular behavior, 2) algorithms that use assessment data to generate intervention messages that address the needs of each user and 3) individual feedback that delivers these messages in a clear and vivid format. Messages will be tailored using the Michigan Tailoring System, an open-source platform developed by the Center for Health Communication Research.

Throughout the first 90 days, if there are less than 3 logins weekly for evening messages noted after 2 consecutive weeks, a message will be sent to inquire how the participant is doing and elicit any problems. At 90, 120, and 150 days, all subjects will be provided the option to continue messages for an additional 30 days. Training for dietitians to facilitate WHEELS-I will be performed by [name], the program's creator. As recommended by the NIH Behavior Change Consortium (Bellg et al. 2004), training will be standardized, delivered by a single trainer, and reinforced (every 6 months). Skill acquisition will be confirmed at baseline and retention by facilitating dietitians observed regularly (e.g., every 10 subjects entering *Phase 2*) by [name]. Receipt of treatment by participants will be assessed via the proportion of messages accessed and responded to. At the end of 16 weeks, all app users will be sent a secure WHEELS-I feedback survey through REDCap, via email. All responses will be automatically uploaded and stored in the secure REDCap application.

The mobile WHEELS application will be downloadable for either iOS or Android from the Apple or Google Play stores, respectively. The participant will receive a unique code to unlock the WHEELS-I application for download. The application will include an overview of DASH/SRD principles, daily notifications and reminders to both influence and measure adherence to the DASH/SRD as above, and positive encouragement for meeting goals. The system will provide a web-based management dashboard for the research team that allows for data collection from the mobile app or email replies, extracts and analysis by the researchers, and adherence to VA security requirements through the use of Amazon.gov cloud hosting.

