The remainder of the outcomes are *Phase 2*-related, i.e. intended to determine longer-term effects of dietary change between the WHEELS and non-WHEELS groups, with both receiving motivational interviewing-based dietary counseling. The primary outcome of *Phase 2* was the change in left ventricular mass index (LVMI, using the Devereaux and Dubois formulas for left ventricular mass and body surface area, respectively) by echocardiography, with secondary outcome of change in PWV, between baseline and end of study participation. These outcomes were assessed using linear regression adjusted for baseline value. Key additional pre-specified outcomes were the change in DASH/SRD adherence measured both by 3-day food diary and Food Frequency Questionnaire (FFQ) and the change in clinic systolic and diastolic blood pressure (BP), between baseline and end of study participation. These were measured using generalized estimating equations to account for repeated within-subject measures over time (baseline/2 weeks and at 1 and 6 months of *Phase 2*) and interaction with WHEELS treatment group assignment. Other pre-specified outcomes were changes in serum triglycerides and urine sodium:potassium ratio between baseline to the end of study, evaluated using 2-sample t-testing.

The sample size for *Phase 2* was set by the participants completing *Phase 1* and influenced by drop-out during the 6 months of the interventions to promote DASH/SRD adoption. We assumed that an additional 10% of subjects will drop out during *Phase 2*, resulting in 90 subjects with evaluable data. The sample size was estimated based on anticipated effects on DASH/SRD adherence, the presumed primary driver of cardiovascular and BP changes in the study. Based on national survey data and our preliminary work, we expected the mean baseline DASH/SRD adherence score by 3-day food diary to be 2.5 ± 1.5 points (scale, 0-9). A sample size of 90 provides >80% power to detect an intra-group change of 0.6 between baseline and the end of study, based on paired t-testing two-sided Type I error of 5%. This sample size provides >80% power to detect a differential between group change in dietary score of 0.9, based on a two-sample t test and two-sided Type I error of 5%.

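### Only the WHEELS arm rehearses reporting its DASH/SRD adherence, the adherence outcome is unblinded self-report, and no Phase 2 analysis compares reported intake with urinary excretion by arm

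*Protocol*

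**What the plan says.** **Arms.** Protocol, Study Phase 2, Dietary intervention: "subjects will be randomized to control (motivational interviewing only) or the addition of the WHEELS-I program". WHEELS-I has three daily activities, the last being "in the evening, record of DASH/SRD adherence during that day". After the first 30 days, "evening messages will continue for the next 60 days"; from day 90 messages continue only if the participant opts in. The application provides "daily notifications and reminders to both influence and measure adherence to the DASH/SRD as above, and positive encouragement for meeting goals". No such log is described for controls.

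**Outcome.** The protocol's primary outcome for Aim 2 is the change in a nine-target concordance score from the FFQ, with 1 point for a target met and 0.5 for an intermediate level. The SAP makes left ventricular mass index the Phase 2 primary and lists among its key additional outcomes the "change in DASH/SRD adherence measured both by 3-day food diary and Food Frequency Questionnaire". It still bases the Phase 2 sample size on the adherence score, taken from the diary.

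**Blinding and handling.** Protocol, Study procedures: "All cardiac and vascular measures will be analyzed blinded to dietary assignment, food diary results, 24-hour BP, and urinary electrolytes". Dietary assessment has no matching statement. Of the diaries, Dietary assessment says "these will be initially reviewed for completeness by the study dietitian"; they are then analysed in nutrient software through a nutrition centre. Elsewhere: "Training for dietitians to facilitate WHEELS-I will be performed by" the program's creator.

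**Urine.** The protocol makes 24-hour urinary sodium the secondary dietary outcome of Phase 2 and tests it with the same t-tests as the score. The SAP tests the urine sodium:potassium ratio by two-sample t-test, in its last group of outcomes, and does not list 24-hour urinary sodium. Using urine to corroborate diary results is described only for Phase 1.

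**The concern.** The arms differ in practice at reporting as well as in help with the diet. One arm spends weeks describing its eating in terms of the DASH/SRD goals, with encouragement for meeting them, and is then scored on a self-report of the same eating pattern. A difference in score may therefore mix a change in eating with a change in reporting.

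The score carries weight in several places. It is the protocol's primary outcome for the WHEELS question and a covariate in its Phase 2 cardiovascular models. In the SAP it is the sizing basis and the presumed driver of the cardiovascular and blood pressure effects. If reporting shifts in one arm only, each of these uses is affected, and the trial could credit WHEELS with better adoption of the diet when only the reports had changed.

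**Working it through.** **1. Does logging overlap outcome collection?** Scheduled evening logging lasts 30 + 60 = about 90 days. The Month 1 diary falls inside that window. The Month 6 FFQ and diary come about 90 days after it ends, unless the participant has opted to continue. So exposure is direct at Month 1. At Month 6 it is either a carried-over habit or optional.

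**2. The plan's own power figure.** Inputs (protocol Phase 2 Sample size and power; SAP): 90 evaluable, 45 per arm, difference 0.9, SD 1.5, two-sided 5%, two-sample t-test. The SD of 1.5 is quoted for the baseline score. Using it for the change implies a baseline to follow-up correlation of 0.5, since SD of change = 1.5 × √(2(1 − ρ)).

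- Standard error = 1.5 × √(2/45) = 1.5 × 0.2108 = 0.316
- Noncentrality = 0.9 / 0.316 = 2.85
- Power (noncentral t, 88 df) = 0.804; normal approximation 0.812

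The stated power above 80% reproduces.

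**3. Same test, no dietary effect, reporting shift in WHEELS only.** The smallest significant observed difference at SD 1.5 is 1.987 × 0.316 = 0.63 points. Replacing 0.9 with an assumed average shift *b* gives these two-sided rejection probabilities (nominal 5%):

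| Shift *b* (points) | SD of change 1.77 (ρ = 0.3) | SD 1.5 (ρ = 0.5) | SD 1.16 (ρ = 0.7) |
|---|---|---|---|
| 0.25 | 10% | 12% | 17% |
| 0.5 | 26% | 35% | 52% |
| 0.75 | 51% | 65% | 86% |
| 0.9 | 66% | 80% | 95% |

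Half a point is one half-step on one of nine targets, averaged over the whole WHEELS arm and net of any over-reporting by controls. The shifts and correlations are assumptions; the documents give neither. The SAP models adherence with generalized estimating equations, not a t-test. The t-test is used here because both documents size the trial on it, and a reporting shift would bias the arm contrast in either analysis.

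**4. How much can the planned urine comparisons settle?** At 45 per arm, 80% power requires a difference of about 0.6 SD (0.9/1.5 from step 2). If the pilot's cross-sectional SDs for urinary sodium, 933 to 1593 mg/24h, are assumed for the change, that is 0.6 × 933 = 560 to 0.6 × 1593 = 956 mg/24h. A null urine result beside a positive score would therefore be ambiguous, and neither document says how it would be read.

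**5. Are the data for a direct comparison there?** The study procedure timeline schedules 3-day diaries and 24-hour urine together at Week 2, Month 1 and Month 6. Diary minus urine sodium and potassium can be formed at each visit without new collection.

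**The case against.** **Urine is already tested between arms.** This stands. The protocol says urinary electrolytes were chosen partly to assess adherence and pairs urinary sodium with the FFQ at Month 6. A reader might infer that nothing planned bears on whether eating changed. That would be wrong, because an effect on reporting alone should leave urine unchanged. What is missing is the direct comparison and a statement on discordant results.

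**The diary reviewer may not be the WHEELS facilitator.** This also stands. A reader might join the two dietitian passages and conclude that they are one person. The documents do not say so. They limit the review to completeness and describe no such review of the FFQ, the protocol's primary instrument. They also require no separation or masking.

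**The arms are closer than they look.** Partly stands. Daily morning messages are assured for 30 days only and may then drop to weekly. Controls also receive the printed diet guide, updates of their cognitive representation of the diet, and counselling. Participants report foods, and the score is computed from nutrients, so they do not rate themselves on the nine targets. The nightly log is still confined to one arm.

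**Logging is part of the intervention.** True. Any change in eating that it causes is a real effect; a change in reporting alone is not.

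**The SAP's primary is echocardiographic and blinded.** True, so that Phase 2 primary is not directly exposed. The protocol's primary for the WHEELS question and the SAP's adherence outcomes are.

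**Conclusion.** The concern holds in a limited form. Nightly adherence logging in one arm, self-report by participants who know their arm, and no stated blinding of dietary assessment leave the score open to differential reporting. The urine comparisons are relevant, but they are kept separate and are sensitive only to large differences. In the SAP they are also reduced to a ratio among its remaining outcomes.

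An average WHEELS-only shift of half a point would raise the false-positive probability from 5% to about 35% at SD 1.5, or 26% to 52% over the assumed correlations of 0.3 to 0.7. These figures rest on 45 per arm, a two-sample t-test and no true dietary difference. They show how sensitive the test is, not that misreporting occurred. A reader might infer that bias large enough to produce the full 0.9-point effect is likely; the documents give no figure for it. This should be corrected because the remedy is cheap and the claim at risk is the main one about WHEELS.

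**What to change.** **SAP, Phase 2 outcomes:**

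- Add an arm comparison of diary intake minus same-visit 24-hour urinary excretion, for sodium and potassium, at Month 1 and Month 6, adjusted for the Week 2 difference. Report the estimate with a confidence interval. Do not make it a pass/fail test of no difference: at 45 per arm, non-significance would not show equal reporting.
- Restore the protocol's between-arm comparison of 24-hour urinary sodium and present it beside the score.
- State that a score gain without urinary support will be described as improved reported adherence.
- State the limits: sodium and potassium cover only part of the nine-target score, and the check applies to the diary, not directly to the FFQ.

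**Protocol, Dietary assessment:** for any diaries still to be processed, carry out completeness review and nutrient coding by study ID with arm withheld, through the existing coding centre.

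The SAP is dated May 2025 and describes the study in the past tense. Masked handling may come too late for most diaries, and the added analysis should be labelled with the date it was added.

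**Cost:** one extra model on data already scheduled, some SAP wording, and possibly a weaker claim if report and urine disagree.

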Dietary intervention: At the week 2 visit, a printed guide to the DASH/SRD produced by the U.S. Department of Health and Human Services will be provided, and participants will complete a standardized questionnaire that establishes their cognitive representation of the DASH/SRD (Scisney-Matlock et al. 2006). Baseline nutrient intake will be assessed with the Block Food Frequency Questionnaire and Nutrition Quest software (NutritionQuest, Berkeley, CA). This instrument has previously been used to assess DASH/SRD concordance (Mellen et al. 2008). Following this visit, participants will consume 14 days of DASH/SRD provided meals, designed by [name]. These will be prepared, pre-packaged, and home-delivered twice weekly by PurFoods, LLC. The study DASH/SRD sodium content will be 50 mmol (1,150 mg/2,100 kcal), as used in the DASH-Sodium study (Sacks et al. 2001). Both diets will be calorie-adjusted to maintain stable body weight using the National Institutes of Health body weight planner (Hall et al. 2011). Nutrient consumption during *Phase 1* will be assessed by 3-day food diary during the second week of each dietary period; results will be corroborated by 24-hour urinary sodium and potassium.

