Sample size and power: The sample size for *Phase 2* is set by the goals of *Aim 1* and influenced by drop-out during the 6 months of the interventions to promote DASH/SRD adoption. We assume that an additional 10% of subjects will drop out during *Phase 2* and that the dropout rate will be equal in salt-sensitive and salt-resistant participants, resulting in 90 subjects with evaluable data. The primary outcome of *Aim 2* of this proposal is the DASH/SRD concordance score from the Block Food Frequency Questionnaire in participants assigned to the WHEELS-I group vs. motivational interviewing alone. Based on national survey data and our preliminary work, we expect the mean baseline (Week 2 visit) dietary score to be 2.5±1.5. A sample size of 90 provides >80% power to detect an intra-group change of 0.6 between baseline and the end of study, based on paired t-testing two-sided Type I error of 5%. This sample size provides >80% power to detect a differential between group change in dietary score of 0.9, based on a two-sample t test and two-sided Type I error of 5%.

With regard to cardiovascular parameters, a sample size of 90 provides >80% power to detect an effect size of 0.6 in the primary endpoint of change from baseline to month 6 in LVMI between salt-sensitive vs. salt-resistant subjects (assuming a 50:50 split of salt sensitive vs. salt-resistant participants), with a two-sided Type I error of

5%. This between-groups comparison is based on a two-sample t test. Conservatively assuming that the standard deviation of the change in LVMI between baseline and 6 months ranges between 4 to 7 g/m2.7 (Blumenthal et al. 2010), this effect size translates to mean group differences of 2.4 to 4.2 g/m2.7. This would represent a 5-10% decrease in LVMI from baseline in salt-sensitive subjects (vs. no change in salt-resistant), similar to that in previous studies of dietary sodium restriction (Jula et al. 1994, Liebson et al. 1995).

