Analysis plan: Paired and 2-sample t-testing will be used to analyze changes in DASH/SRD concordance score as above, as well as changes in 24-hour urinary sodium excretion. The methods to analyze cardiovascular changes in *Aim 2* will be identical to those used in the comparison of salt sensitivity phenotypes in *Aim 1* (see above). Important covariates in the models to compare changes in cardiovascular parameters by salt-sensitive/resistant phenotype will be the degree of DASH/SRD concordance and changes in 24-hour BP.

Potential problems/alternative approaches: While motivational interviewing and the WHEELS-I program have been effective in our preliminary studies, we expect individual variance in DASH/SRD adoption. The primary analysis will be an intent-to-treat framework; secondary analyses will test interaction with the level of DASH/SRD adoption. (Mellen et al. 2008) We expect that participants who successfully adopt DASH/SRD will substantially change their eating habits. The WHEELS-I program does not target weight loss, but since sodium intake correlates with caloric intake (Guenther et al. 2013) it is possible that some veterans may lose weight during *Phase 2*. We do not a *priori* expect differential weight loss in salt-sensitive and salt-resistant subjects. However, since cfPWV and LVMI can both be reduced through weight loss, we will perform analyses adjusted for *Phase 2* weight changes (Blumenthal et al. 2010). If the proportions of salt-sensitive and salt-resistant subjects are not equal (say 60%:40%), we would retain >80% power to detect effect size of 0.61.

Specific Aim 3 (spans Study Phases 1 and 2): Determine effects of DASH/SRD feeding and longer-term adoption on microvascular function, and assess the relationship between endothelial glycocalyx integrity/sodium buffering and cardiovascular response to DASH/SRD.

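### Phase 2 t tests on change leave out the baseline covariate that the SAP already uses for LVMI and PWV: a low-severity, nearly free gain in precision

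*Protocol*

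**What the plan says.** **Protocol, Phase 2.** Half of participants are randomised to WHEELS-I on top of motivational interviewing. The primary outcome of Aim 2 is change in DASH/SRD concordance score; the secondary dietary outcome is change in 24-hour urinary sodium. The Phase 2 Analysis plan states: "Paired and 2-sample t-testing will be used to analyze changes in DASH/SRD concordance score as above", and extends this to urinary sodium. It names no baseline covariate. The Sample size and power paragraph says "we expect the mean baseline (Week 2 visit) dietary score to be 2.5±1.5" and "This sample size provides >80% power to detect a differential between group change in dietary score of 0.9", with 90 evaluable participants.

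**SAP, Phase 2 outcomes** (dated May 31, 2025). Three methods serve the same randomised contrast:

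- LVMI and PWV: "These outcomes were assessed using linear regression adjusted for baseline value".
- DASH/SRD adherence (food diary and FFQ) and clinic BP: "generalized estimating equations to account for repeated within-subject measures over time". Baseline/2 weeks is listed among the time points, with an interaction with WHEELS assignment.
- Other outcomes: "changes in serum triglycerides and urine sodium:potassium ratio between baseline to the end of study, evaluated using 2-sample t-testing".

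The SAP does not list 24-hour urinary sodium as an outcome. The t test on the diet score survives there only in the power statement.

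**The concern.** Under 1:1 randomisation, adjusting for a baseline taken before randomisation is, in large samples, never less precise than comparing change scores. It also removes chance baseline imbalance, which matters with about 45 per arm. The baselines are already scheduled, and randomisation follows Phase 1, so they are valid covariates. The SAP applies this method to LVMI and PWV and gives no reason for withholding it from sodium:potassium ratio and triglycerides.

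The GEE is a related but softer point. Baseline enters as a repeated response. The SAP does not say whether the arms share one baseline mean, or which working correlation is used. Those two choices decide whether the baseline information is used or given up.

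At stake are wider confidence intervals than necessary. Bias and type I error are not in question.

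**Working it through.** **Inputs.** From the documents: 90 evaluable, hence 45 per arm; difference 0.9 points; two-sided 5%; SD 1.5, given for the baseline score only (Protocol, Phase 2 Sample size and power). Not documented: the SD of change, the month-6 SD, and the baseline-to-month-6 correlation ρ for any of these outcomes. The 0.70 in the Phase 1 sample-size paragraph is for cfPWV.

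**1. The plan's own figure.** Two-sample t test, 45 per arm, SD of change 1.5 (assumed), noncentral t with 88 df: power 80.4%, detectable difference at 80% power 0.90. The stated figure of more than 80% reproduces. With equal SDs at both visits, an SD of change of 1.5 implies ρ = 0.5, since 1.5·√(2(1−0.5)) = 1.5.

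**2. Validity.** In 20,000 simulated trials at ρ = 0.5, type I error was 4.98% for both the change-score t test and baseline-adjusted regression. With a true difference of 0.9, both averaged 0.899. The empirical SE was 0.317 for change and 0.275 for adjusted.

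**3. Gain with equal SDs (illustration).** SD of change = 1.5·√(2(1−ρ)); adjusted residual SD = 1.5·√(1−ρ²). The share of variance saved is (1−ρ)/2. Adjusted power uses 87 df.

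| ρ | SD change | SD adjusted | Variance saved | Power for 0.9: t → adjusted | Detectable difference |
|---|---|---|---|---|---|
| 0.5 | 1.500 | 1.299 | 25% | 80.4% → 90.1% | 0.90 → 0.78 |
| 0.6 | 1.342 | 1.200 | 20% | 88.2% → 94.0% | 0.80 → 0.72 |
| 0.7 | 1.162 | 1.071 | 15% | 95.3% → 97.6% | 0.69 → 0.64 |

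If the SD of change is instead held at 1.5, adjusted power falls towards the t test's 80.4% as ρ rises: 86.3% at ρ = 0.7 and 82.3% at ρ = 0.9.

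**4. Sensitivity to unequal SDs.** Saving = 1 − s₂²(1−ρ²)/(s₁² + s₂² − 2ρs₁s₂), with s₁ = 1.5 at baseline and s₂ at month 6.

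| s₂ | ρ = 0.5 | ρ = 0.7 |
|---|---|---|
| 1.0 | 57.1% | 55.7% |
| 1.5 | 25.0% | 15.0% |
| 1.8 | 12.9% | 3.4% |
| 2.0 | 7.7% | 0.5% |

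**5. Urinary sodium (Protocol t test only).** The Preliminary Data give two SD pairs. The counselling study (40 and 39 mmol) gives savings of 26.9% to 17.2% for ρ of 0.5 to 0.7. The provided-meal pilot (1593 and 933 mg) gives about 66% over the same range.

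**6. GEE.** Large-sample variance of the month-6 contrast relative to a change score, with baseline, Month 1 and Month 6, equal SDs and complete data:

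| Mean model and working correlation | ρ = 0.5 | ρ = 0.7 |
|---|---|---|
| Unconstrained time-by-group, exchangeable | 1.00 | 1.00 |
| Common baseline mean, exchangeable | 0.75 | 0.85 |
| Common baseline mean, independence | 1.00 | 1.67 |

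The middle row equals the baseline-adjusted regression. With 10% of month-6 values missing completely at random, the unconstrained model improves only to 0.967 and 0.971; the common-baseline model gives 0.742 and 0.836. For the FFQ, Figure 8 schedules no Month 1 collection. There are then only two time points up to month 6, and on complete data an unconstrained GEE is exactly a change-score comparison.

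**The case against.** Several points on the other side stand.

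- The Protocol t tests are not all current. The SAP analyses the score by GEE and lists sodium:potassium ratio, not urinary sodium. A reader might infer that all four outcomes will be t-tested; in the SAP only sodium:potassium ratio and triglycerides are, both in its last group of other outcomes.
- The figures above are for the score and urinary sodium. For the two outcomes still t-tested in the SAP, no size can be given.
- The SAP already adjusts its Phase 2 primary and secondary outcomes, LVMI and PWV.
- A reader might infer that the GEE ignores baseline. It does not: baseline is a listed repeated measure. Only the equal-baseline constraint and the working correlation are open, and one ordinary specification loses nothing.
- The advantage of adjustment is asymptotic. Estimating the slope inflates variance by roughly 1/(90−4) = 1.2%, which would outweigh a 0.5% saving.
- The 66% for urinary sodium comes from 13 people with heart failure eating provided meals. Phase 2 uses counselling, so the 40/39 mmol pair is the closer guide.

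What these points do not remove is that two SAP comparisons omit a covariate the SAP uses elsewhere, and that the GEE is not specified enough to show whether it recovers the same precision.

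**Conclusion.** The point holds as a low-severity, precision-only improvement. It applies directly to sodium:potassium ratio and triglycerides in the SAP, and to FFQ score and urinary sodium wherever the Protocol t test is used. For adherence and clinic BP under GEE the loss is conditional on the unstated model form.

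Two stronger readings should be resisted. One is that the t tests are biased or invalid: assignment is randomised after baseline, and the simulation shows nominal type I error and the correct mean. The other is that the between-group comparison is underpowered. With equal SDs and ρ = 0.3 the t test would have 66% power and adjusted regression 84%, but the documents give no ρ, and the stated power is met under the plan's apparent SD of change of 1.5.

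The size is undocumented. For the score, 80% to 90% at ρ = 0.5 and 95% to 98% at ρ = 0.7 are illustrations that assume SD 1.5 at both visits. They are not bounds, and the gain can be near zero if the month-6 SD is larger. No figure is claimed for sodium:potassium ratio, triglycerides or BP.

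**What to change.** 1. **Sodium:potassium ratio and triglycerides (SAP), and FFQ score and urinary sodium wherever the Protocol t test is used:** regress the month-6 value on WHEELS arm and the pre-randomisation baseline, as for LVMI and PWV. Using change as the response gives the same arm coefficient, so the planned between-group contrast is kept.
2. **Adherence scores and clinic BP:** either model the post-randomisation values with baseline as a covariate (Months 1 and 6 for diary score and BP; Month 6 for the FFQ), or state a GEE with a common baseline mean and an exchangeable or unstructured working correlation. Under independence, the common-baseline GEE compares raw month-6 means and recovers nothing.
3. **Define the covariate as the baseline actually collected.** For the FFQ, Study procedures says "collected at screening and at the end of study", as does Figure 8 for the first collection. The Phase 1 Dietary intervention paragraph, describing the week 2 visit, says "Baseline nutrient intake will be assessed with the Block Food Frequency Questionnaire", and the Phase 2 power paragraph also uses week 2. The Protocol attaches the 2.5±1.5 score to the FFQ and the SAP to the food diary. These are separate consistency points that add no weight here, but the covariate cannot be defined until they are settled.

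**Cost:** SAP wording, a re-run of existing models and one degree of freedom per model; no new data. The SAP is dated 2025 and written in the past tense. If results by arm have already been seen, report the adjusted analysis as a labelled supplement beside the planned one, not as its replacement.
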